Trained research staff blinded to participants’ tDCS assignment performed pre- and post-intervention assessments. Follow-up assessments were performed within two weeks of completing the intervention. Feasibility was assessed by examining participants’ in-class attendance (i.e., number of in-person MBSR group sessions attended) and adherence to at-home mindfulness practice while using tDCS. Participants completed hand-written logs daily, detailing their at-home use of tDCS and the frequency and duration of MBSR practice; these self-report logs were used to determine the at-home adherence rates. To determine the at-home adherence rate, we first determined how many at-home sessions each participant completed by looking through the at-home logs. We then calculated the

total expected number of sessions that should have been completed at home over the period of the intervention. Lastly, we divided the total number of sessions each participant completed by the total number of expected sessions to get a percentage of at-home adherence. Participants also documented any failures of the tDCS device during stimulation and any adverse events (AEs). AEs that required the discontinuation of tDCS or MBSR were identified, as were serious adverse events (SAEs) defined as AEs that resulted in life-threatening health issues, hospitalization, or death.

The main cognitive measure was the Fluid Cognition Composite from the National Institutes of Health (NIH) Toolbox Cognition Battery [38], a computer-based instrument measuring both crystallized and fluid cognition. In addition, immediate memory and delayed recall were measured using a standard 16-word list validated at the Washington University Alzheimer's Disease Research Center that is sensitive to change and does not have ceiling effects in preliminary studies.

The Cognitive Affective Mindfulness Scale – Revised (CAMS-R; [39]) was used to measure the four domains of mindfulness – attention, present-focus, awareness, and acceptance. CAMS-R is a self-report measure of everyday mindfulness that is not specific to any one type of meditation. CAMS-R asks questions about translating and integrating the domains of mindfulness into everyday life, for example, being able to focus on the present moment, and keeping track of one's thoughts and feelings. CAMS-R

was administered pre- and post-intervention to determine how well participants integrated the teachings from MBSR into their everyday lives.

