In addition to the PROMIS measures of depression and anxiety, the two following PROMIS measures were used to assess satisfaction with, and ability to perform usual social roles and activities: the 8-item short form v2.9 PROMIS Scale for Satisfaction with Social Roles and Activities [40] and the 8-item short form v2.0 PROMIS Ability to Participate in Social Roles and Activities [40].

Statistical Analyses

All data were analyzed using the Statistical Program for Social Sciences (SPSS) version 25.0 [41]. Extreme outliers (± 3 standard deviations) were removed for each time point. Data were visually inspected for normal distribution and were checked statistically with the Shapiro-Wilk test. Chi-square and independent samples *t*-tests were used to evaluate differences between the active and sham tDCS groups on baseline demographic, clinical, and cognitive measures.

Measures of feasibility, tolerability, and safety were analyzed descriptively. While the primary goal of this pilot study was to assess feasibility, tolerability, and safety, preliminary evaluations of changes in efficacy measures were performed using repeated measures analyses of variance (RM-ANOVAs), with randomization as the between-subjects variable, and time-point (pre- or post-intervention) as the within-subjects

variable. For cognition, the three dependent variables were: NIH Toolbox Cognition Battery Fluid Cognition Composite, total recall score of the word list, and the delayed recall score of the word list. The effects of the intervention on subjective changes were explored with the following five dependent variables: CAMS-R, PROMIS depression scores, PROMIS anxiety scores, PROMIS satisfaction with social roles and activities, and PROMIS ability to participate in social roles and activities. For this pilot trial, a $p < 0.05$ was considered significant and no corrections were made for multiple comparisons.

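### Values beyond ±3 SD, post-intervention outcomes included, are removed with size as the only stated criterion; the reference SD, the unit removed and an all-data analysis are not described (minor)

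*Combined protocol and SAP*

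**What the plan says.** All of the relevant text is in the Statistical Analyses section of the combined protocol and SAP, apart from the description of the measures under Outcomes.

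- The rule: "Extreme outliers (± 3 standard deviations) were removed for each time point".
- The next sentence: "Data were visually inspected for normal distribution and were checked statistically with the Shapiro-Wilk test". It gives no action to take if normality fails.
- The efficacy model: "repeated measures analyses of variance (RM-ANOVAs), with randomization as the between-subjects variable, and time-point (pre- or post-intervention) as the within-subjects" variable. It is applied to three cognitive and five subjective dependent variables, eight in all.
- The status of efficacy: "While the primary goal of this pilot study was to assess feasibility, tolerability, and safety, preliminary evaluations of changes in efficacy measures were performed". The feasibility, tolerability and safety measures are analysed descriptively.
- The threshold: p < 0.05 "was considered significant and no corrections were made for multiple comparisons".
- Independent-samples t-tests compare the arms on baseline clinical and cognitive measures, among others.

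The wording of the rule suggests that the SD is computed separately at each time point. It does not say whether that SD is pooled over the arms or taken within each arm. Nor does it say whether what is removed is the single value or the whole participant. The documents give no sample size, no SD and no count of removals.

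**The concern.** The time points in the model are pre- and post-intervention, so the rule reaches outcomes measured after randomisation. A two-time-point RM-ANOVA uses only participants with both values. Removing a post-intervention score therefore excludes a randomised participant from that outcome because of the result observed. The text describes no step that separates an entry or administration error from a genuine extreme response.

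The two open definitions matter for reproducibility. If single values are removed, the eight comparisons can rest on different subsets. If whole participants are removed, the subset is common to all, but one extreme score on one measure costs that person all eight outcomes. A pooled and a within-arm SD also flag different values, and in small arms the within-arm rule cannot act at all.

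At stake is whether a reader can tell which of the eight verdicts, each read at 0.05 without correction, depends on the removals. Pre-intervention values are also covered, so the baseline t-tests may be touched. Attendance, adherence and adverse events are not pre/post scores in this model, so the primary goal is not at issue.

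**Working it through.** There is no stated figure to reproduce. What follows is illustrative and rests on assumptions.

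**1. When the rule can act.** The largest possible |z| in a sample of n is (n − 1)/√n.
- n = 10: 9/3.162 = 2.85
- n = 11: 10/3.317 = 3.02
- n = 20: 19/4.472 = 4.25

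With 10 or fewer per arm, a within-arm rule can never remove anything; a rule pooled over 20 can.

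**2. Simulation inputs.** From the documents: 1:1 allocation, two time points, eight outcomes, threshold 0.05. Assumed: 14, 20 or 30 per arm; pre/post correlation 0.6; normal scores; a uniform 0.40 SD effect; outcomes correlated 0.5. The group-by-time test was run as a t-test on change, on all data and again after ±3 SD removal at either time point. There were 40,000 replicates per setting (20,000 for eight outcomes).

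**3. Bias and type I error.** With normal data and a uniform effect the mean estimate stays at 0.40. With no effect, type I error at 14/20/30 per arm is:
- all data: 5.07/5.01/5.00%
- after pooled-SD removal: 5.08/5.00/5.03%
- after within-arm removal: 5.07/5.09/5.12%

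**4. How often verdicts change (pooled SD, 0.40 SD effect).**

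| | 14 per arm | 20 per arm | 30 per arm |
|---|---|---|---|
| One outcome loses someone | 5.6% | 11.2% | 19.8% |
| One outcome's verdict changes (value removed) | 0.42% | 0.89% | 1.41% |
| At least one of eight changes: value removed, unbounded | 3% | 7% | 11% |
| At least one of eight changes: participant removed, unbounded | 12% | 22% | 32% |
| At least one of eight changes: value removed, 0–16 scores | 1.0% | 1.6% | 2.2% |
| At least one of eight changes: participant removed, 0–16 scores | 4.5% | 7.0% | 10.1% |

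As a hand check on the third row, treating outcomes as independent, 1 − (1 − p)^8 with p = 0.0042, 0.0089 and 0.0141 gives 3.3%, 6.9% and 10.7%.

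The single-outcome changes go both ways. To significant: 0.18/0.37/0.53%. To non-significant: 0.24/0.52/0.87%.

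**5. Why bounded scores matter.** The 0–16 rows assume rounded scores with mean 8 and SD 3 in all eight outcomes (10,000 replicates). The nominal limits are 8 ± 9, that is −1 to 17, outside the scale. Removal then needs a sample mean or SD away from those values, and the effect is roughly 2.5 to 5 times smaller.

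**6. Other settings, at least one of eight verdicts changed.**
- No effect, pooled SD, unbounded: 1.3/2.3/3.8% (values) and 5.5/8.3/11.3% (participants).
- No effect, pooled SD, 0–16 scores: 0.4/0.6/0.7% and 2.4/2.9/3.2%.
- Within-arm SD, 0.40 SD effect, unbounded: 0.3/2.5/7% and 1/9/23%.

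**7. Departures from normality.** With a 0.5 SD effect and total N up to 60, one outcome's verdict differed in up to 15% of trials with t(3) data and up to 22% with log-normal data. For log-normal data with a within-arm SD and no effect, type I error at N = 60 was 6.6%, against 4.4% with all data. The documents neither support nor exclude such shapes.

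**The case against.** The strongest case on the other side is that this is a short methods text for a pilot, efficacy is labelled preliminary, the lack of multiplicity correction is disclosed, and ±3 SD is a common rule. With near-normal data it does no average harm. The largest figures need three things the documents do not give: unbounded scores, a 0.40 SD effect in all eight outcomes and, for the 12–32% range, removal of whole participants. The rule reads most directly as removing values. Most of the measures, such as the 16-word list and the 7- and 8-item PROMIS forms, have finite ranges. Nor does the plan say that any one significant outcome out of eight counts as success.

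Most of this stands, and it is why the point is minor. It does not supply the missing definitions or counts, and it does not alter the fact that the recorded rule can exclude people on a post-randomisation result.

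A reader might infer more than the documents support:

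- **That no error check or all-data analysis was done.** The text only fails to describe them; silence is not evidence that they were omitted.
- **That the efficacy results are biased or false positives inflated.** The rule as written does not refer to arm, and the near-normal simulations show neither.
- **That real benefit was trimmed away.** If the 0.40 SD mean effect came from a 3 SD gain in 13% of the active arm, pooled removal would understate it by 10/13/15% at 14/20/30 per arm. Nothing in the documents points to that pattern, and a bounded scale may not allow such a gain.

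**Conclusion.** The point holds as an undisclosed sensitivity of the preliminary efficacy results, not as a demonstrated bias. Size is the only stated criterion for removal, post-intervention outcomes are included, and two definitions needed to reproduce the analysis are missing. The normality checks settle neither.

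On the more natural reading, with values removed on a pooled SD, any one verdict changes in about 0.4–1.4% of trials. At least one of eight changes in about 3–11% with unbounded scores or 1–2% with 0–16 scores. If whole participants were removed, the figures are about 12–32% or 4–10%. All of these assume 14 to 30 per arm, near-normal data and a 0.40 SD effect. They are lower with no effect or a within-arm SD, and could be higher with skewed or heavy-tailed data.

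The reach is the eight efficacy comparisons and possibly the baseline t-tests. The primary feasibility, tolerability and safety goal is unaffected. Severity: minor. Confidence in the sizes is moderate, because the sample size and score distributions are not given.

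**What to change.** Keep the sentence that records what was done and add the two definitions:

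> The SD was taken [over both arms / within arm] at each time point, and [the single value / the whole participant] was removed.

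Then add, labelled as post hoc:

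> Each of the eight efficacy RM-ANOVAs is re-run on all observed values, excluding only values confirmed as entry or administration errors, reviewed without reference to arm where feasible. Both sets of results are shown side by side, with the number removed per outcome, arm and time point. Any efficacy result that differs between the two is described as sensitive to outlier removal. Neither analysis replaces the other.

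If baseline values were removed before the baseline t-tests, say so in the same place.

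The cost is two clarifying phrases, eight re-runs on existing data and one table of removals. The all-data run will be slightly less precise if tails are heavy for reasons unrelated to treatment. Because it is added after the fact, it should inform the reading of the reported results and not overrule them. Error review without knowledge of arm may no longer be fully possible now that the analysis is complete; if so, that should be stated.

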Thursday June 3rd, 2021

TITLE: Enhancing Cognition in Older Persons: A Randomized Controlled Trial of Mindfulness-Based Stress Reduction (MBSR) and Transcranial Direct Current Stimulation (tDCS).

NCT03653351

METHODS

Study design and participants

We conducted a randomized, double blind, sham-controlled trial of tDCS combined with MBSR in adults aged 60 years or older with symptoms of depression or anxiety plus subjective cognitive complaints in two academic centers (Centre for Addiction and Mental Health, Toronto, ON, Canada; and Washington University in St. Louis, MO, USA). The study was approved by both institutional review boards and all participants provided written informed consent.

Participants were recruited between June 27, 2018 and March 6, 2019. They completed an initial phone screen followed by an in-person screening assessment, which included a review of medical history and medications to determine eligibility. Participants reported cognitive complaints but had intact cognitive function as ascertained by a Short Blessed Test [27] score ≤ 10 and a Montreal Cognitive Assessment (MoCA; [28]) score ≥ 25 . The Patient Reported Outcomes Measurement Information System (PROMIS) measures were used to assess depression and anxiety over the past seven days [29] including self-reported negative mood, views of self, social cognition, decreased positive affect, engagement self-reported fear, anxious misery, hyperarousal, and somatic symptoms related to arousal [30]. Participants were included if their baseline PROMIS 8-item depression score was ≥ 16 or their baseline PROMIS 7-item anxiety score was ≥ 14 , indicating moderate to severe symptoms.

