Exclusion criteria included unstable medical illness, metal implants, significant neurological conditions, use of cognitive enhancers (e.g., donepezil) within the past 6 weeks, use of anticonvulsants or antipsychotics (other than low-dose aripiprazole (\leq 2mg) or low dose gabapentin (\leq 100mg) if prescribed for pain), current cognitive training with brain training software, regular participation in mindfulness practice or yoga, IQ $<$ 70 as estimated by the Wechsler Test of Adult Reading (WTAR; [31]), lifetime diagnosis of bipolar disorder, schizophrenia, schizoaffective disorder, or untreated post-traumatic stress disorder, or substance abuse within six months, as diagnosed by the Mini-International Neuropsychiatric Interview (MINI; [32]). Participants meeting all eligibility criteria completed the baseline assessments, which included self-report and neuropsychological assessments of outcomes, listed below.

Interventions

All participants received MBSR; they were randomly assigned (1:1) to active or sham tDCS, using a permuted block approach to ensure treatment balance within each study site. Participants, MBSR instructors, and outcome raters were blinded to the tDCS condition (i.e., active vs. sham). Following the protocol of a large trial assessing the efficacy of combining tDCS with cognitive remediation in preventing dementia among older adults with mild cognitive impairment or remitted depression [33], active tDCS administration involved applying excitatory bilateral stimulation to the left and right DLPFC. To achieve this bilateral stimulation, the anode was placed at Fz and the cathode at Iz as per the 10-20 international electrode placement system. The tDCS was applied using a direct current of 2 mA (current density of 0.57 A/m^2) for 30 minutes per day [33].

during meditative practices of MBSR. The same parameters were used for sham stimulation, except the device shut off after 30 seconds of active stimulation. This brief period of active stimulation is not known to produce active neurological effects, but does ensure blinding because it is associated with common side effects of active tDCS, such as tingling and itching under the electrodes [34-36].

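### The active-versus-sham comparison uses a two-time-point RM-ANOVA, which amounts to a change-score test; adjusting for baseline and the blocking factor would usually be more precise

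*Combined protocol and SAP*

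**What the plan says.** The efficacy model is in Statistical Analyses: "preliminary evaluations of changes in efficacy measures were performed using repeated measures analyses of variance (RM-ANOVAs), with randomization as the between-subjects variable". The other factor is "time-point (pre- or post-intervention) as the within-subjects" variable. The model is applied to eight measures: three cognitive and five self-reported. The section does not say whether the arm main effect or the arm-by-time interaction is the treatment contrast, and it names no covariate.

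On allocation, Interventions says that "they were randomly assigned (1:1) to active or sham tDCS", "using a permuted block approach to ensure treatment balance within each study site". There are two sites, and site is not in the stated model.

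Baseline comparability is handled by testing: "Chi-square and independent samples *t*-tests were used to evaluate differences between the active and sham tDCS groups on baseline demographic, clinical, and cognitive measures". No adjustment follows from those tests.

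The same section makes feasibility, tolerability and safety the primary goal, analysed descriptively, and calls the efficacy work preliminary. It nevertheless applies p < 0.05 to each efficacy measure.

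**The concern.** The interaction is the RM-ANOVA term that measures an arm difference in change. With two time points it is the change-score t-test, which fixes the slope of post on baseline at 1. The slope is usually below 1, so subtracting the whole baseline over-corrects. Over repeated randomisations the estimate is unbiased but more variable than it needs to be. In any single small trial it moves with whatever baseline gap chance produced. These are two views of one cost, not two separate harms.

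The unnamed term adds some risk. The arm main effect is a test on the average of the pre and post scores, which halves any post-treatment effect. A reader who took that as the treatment test would have much less power.

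Every participant received MBSR, so the active-minus-sham differences are the only randomised evidence on tDCS efficacy that the trial gives. Their intervals should be as narrow as the collected data allow.

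**Working it through.** **Inputs from the plan.** Two time points, 1:1 allocation, two sites with blocking within site, eight measures, α = 0.05. The plan gives no sample size, effect size, SD or pre-post correlation, so it has no figure to reproduce.

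**Assumed inputs.** Total N = 20, 28 or 40; ρ = 0.5 to 0.9; equal pre and post SDs (set to 1); two-sided tests; no true site effect.

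**Step 1: the identity.** In a simulated data set with 13 per arm, the split-plot arm-by-time F was 0.6556 and the squared t on change was 0.6556 (p = 0.426 for both). The arm main-effect F equalled the squared t on the pre-post average (1.0752 both ways).

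**Step 2: variance of the arm difference.**
- Change score: (4/N) × 2(1 − ρ).
- ANCOVA with baseline and site: (4/N) × (1 − ρ²) × (N − 4)/(N − 5).
- Ratio, ANCOVA to change score: [(1 + ρ)/2] × (N − 4)/(N − 5).

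At N = 28 and ρ = 0.5 the ratio is 0.75 × 24/23 = 0.783, a saving of 22%.

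| Variance saving | ρ = 0.5 | 0.7 | 0.8 | 0.9 |
|---|---|---|---|---|
| N = 20 | 20% | 9% | 4% | −1% |
| N = 28 | 22% | 11% | 6% | 1% |
| N = 40 | 23% | 13% | 7% | 2% |

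A simulation of 15,000 trials per cell at N = 28 gave ratios of 0.783, 0.891, 0.938 and 1.000. Both estimators were unbiased. Type I error at ρ = 0.5 was 0.050 (change score) and 0.052 (ANCOVA).

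**Step 3: break-even.** On variance, ρ = 2(N − 5)/(N − 4) − 1, which is 0.88, 0.92 and 0.94 for N = 20, 28 and 40. On interval width, which also counts the larger t quantile (df N − 4 instead of N − 2), break-even is 0.84, 0.90 and 0.94.

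**Step 4: intervals and power at N = 28 (change score → ANCOVA).** For ρ = 0.5 the half-widths are 2.056 × √0.1429 = 0.78 and 2.064 × √0.1118 = 0.69. Power is from the non-central t.

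| | ρ = 0.5 | 0.7 | 0.8 | 0.9 |
|---|---|---|---|---|
| 95% half-width (SD) | 0.78 → 0.69 | 0.60 → 0.57 | 0.49 → 0.48 | 0.35 both |
| Power, 0.8 SD | 53% → 63% | 75% → 80% | 90% → 91% | 99.5% both |

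For smaller effects the gain at ρ = 0.7 is slight: 38% → 41% for 0.5 SD and 17% → 18% for 0.3 SD. The arm main effect, by contrast, rejected about 21% of the time for a true 0.8 SD at ρ = 0.5.

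**Step 5: chance imbalance.** The probability of a baseline gap of at least 0.4 SD on a given measure is 2[1 − Φ(0.4/√(4/N))], which is 29% at N = 28 and 21% at N = 40. Over eight measures the expected count is 8 × 0.29 = 2.3 or 8 × 0.21 ≈ 1.6. A 0.4 SD gap shifts the change-score estimate by 0.4 × (1 − ρ), that is 0.12 SD at ρ = 0.7 and 0.20 SD at ρ = 0.5. In simulation the ANCOVA estimate did not move with the gap.

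**Step 6: unequal variances at N = 28.**
- If the entry cut-offs halved baseline variance, the ratio for slope b is (1 − b²)/[0.5(1 − b)² + (1 − b²)] × 24/23. That is 0.89 at b = 0.5 and 0.96 at b = 0.7, so savings of 11% and 4%.
- If the post SD were 1.15 times the pre SD, the savings would be about 12%, 1% and −3% at ρ = 0.5, 0.7 and 0.8. A smaller post SD would raise them.

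**The case against.** The strongest case is that nothing here is wrong. The RM-ANOVA is valid, the plan says it is evaluating changes, the natural reading of a two-factor RM-ANOVA is the interaction, and efficacy is preliminary in a pilot with descriptive primary aims. All of that stands, and it limits the importance of the point. It does not remove it, because the plan still tests eight efficacy measures at p < 0.05 and a tighter estimate is available from the same data.

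The gain is also conditional. It is negligible for very stable measures, small at ρ = 0.8, and can vanish or reverse if post scores are more variable than baseline scores. This stands too, and is why the claim is that adjustment *usually* helps.

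No precision gain from site has been shown. Change scores already cancel stable site differences, and the calculations assume no site effect. The case for site is therefore that it was the blocking factor; its one degree of freedom is already charged in the figures.

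Finally, the document is dated June 2021 and describes finished work, so replacing the contrast now is post hoc. That calls for labelling, not for leaving the analysis out.

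**Conclusion.** The concern holds, as a matter of efficiency and not of validity. The plan's arm contrast is a change-score test without the baseline covariate or the blocking factor. At N = 28 with equal SDs, the avoidable variance is about 11% to 22% for ρ = 0.7 to 0.5, falling to 1% at ρ = 0.9. Above a ρ of roughly 0.84 to 0.94, depending on N, intervals would not narrow. N, ρ, effect size and equal SDs are all assumptions, and unequal SDs can lower or raise the saving. The change should be made, since it costs very little, but no primary conclusion of the trial depends on it.

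**What to change.** 1. For each of the eight measures, fit an ANCOVA of the post score on arm, the baseline value of the same measure, and site. Report the adjusted active-minus-sham difference with its 95% CI. Use participants with both values and state how many there are, because the plan says "Extreme outliers (± 3 standard deviations) were removed for each time point" and that can leave only one of a pair.
2. Name this difference as the arm contrast, so that the RM-ANOVA arm main effect is not read as the treatment effect.
3. Keep the RM-ANOVA time effect, with its CI, as pooled pre-post change. It serves aims such as that of the CAMS-R, which was "administered pre- and post-intervention to determine how well participants integrated the teachings from MBSR into their everyday lives". Label it uncontrolled. For PROMIS depression and anxiety, note the entry rule, "Participants were included if their baseline PROMIS 8-item depression score was ≥ 16 or their baseline PROMIS 7-item anxiety score was ≥ 14": selection on a high baseline score can by itself produce a later fall.
4. Optionally, present baseline characteristics by arm without significance tests. The main change does not depend on this.

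The cost is two degrees of freedom per model (baseline and site) and eight models re-run on data already collected. The analysis should be reported as post hoc. The feasibility, tolerability and safety analyses do not change.

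### The RM-ANOVA does not name which term tests tDCS; the natural choice, arm-by-time, is valid but takes no account of baseline, and the time term has no control because everyone receives MBSR

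*Combined protocol and SAP*

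**What the plan says.** The Interventions section of the combined protocol and SAP sets the design: "All participants received MBSR; they were randomly assigned (1:1) to active or sham tDCS". Allocation used permuted blocks within each of two sites.

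The Statistical Analyses section says that "preliminary evaluations of changes in efficacy measures were performed using repeated measures analyses of variance (RM-ANOVAs), with randomization as the between-subjects variable". The repeated factor is time, at two levels: before and after the intervention. There are three cognitive and five subjective dependent variables, hence eight models, each judged at p < 0.05. The subjective set is introduced with "The effects of the intervention on subjective changes were explored with the following five dependent variables". No model term is named as the efficacy test, and neither a baseline covariate nor a site term is mentioned. Baseline enters only as the first level of the repeated response.

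Separately, chi-square and t-tests "were used to evaluate differences between the active and sham tDCS groups on baseline demographic, clinical, and cognitive measures". No stated analysis makes use of their result.

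The Outcomes section says that the CAMS-R "was administered pre- and post-intervention to determine how well participants integrated the teachings from MBSR into their everyday lives".

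On the timing of the PROMIS scores, the Study design and participants section calls the score used for entry the baseline score. The same section then says "Participants meeting all eligibility criteria completed the baseline assessments, which included self-report and neuropsychological assessments of outcomes".

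The analysis is reported as already done: "All data were analyzed using the Statistical Program for Social Sciences (SPSS) version 25.0".

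**The concern.** Two things are left open in the way the plan gets from the design to a statement about efficacy.

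- **Which term.** A two-arm, two-time-point RM-ANOVA produces three tests. Arm-by-time compares change between randomised arms. The arm main effect averages the pre and post scores, which dilutes any effect. The time main effect pools both arms and has no control, because nobody goes without MBSR. It mixes any MBSR effect with retest practice, expectancy and the passage of time. The intervention is not defined as tDCS alone, and the stated purpose of the CAMS-R is a pre-post question about MBSR. The plan therefore leaves room for a time effect to be read as efficacy.
- **How baseline is used.** With two time points, arm-by-time is the t-test on change scores. It does not adjust for baseline, so a chance difference between arms at baseline carries partly into the estimate, even when the planned baseline test would not flag it.

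At stake are the precision and the interpretation of the preliminary efficacy estimates, not the feasibility, tolerability and safety aims.

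**Working it through.** The documents state no sample size, power, effect size or correlation, so there is no figure to reproduce. What follows is illustration on assumed inputs: total N of 20, 28 or 40 in equal arms, pre-post correlation r from 0.3 to 0.9, SD of 1 at both times, two-sided 5%, no dropout. The site term is left out of these calculations.

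**1. Precision of the tDCS contrast.** The variance factor is 2(1−r) for arm-by-time and 1−r² for the post score adjusted for baseline. Their ratio is (1−r²)/[2(1−r)] = (1+r)/2. Estimating the slope multiplies this by (N−3)/(N−4), which is 25/24 at N=28, 37/36 at N=40 and 17/16 at N=20. Power is for a true effect of 0.5 SD.

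| N | r | Variance ratio, adjusted to arm-by-time | Power, arm-by-time | Power, adjusted |
|---|---|---|---|---|
| 28 | 0.3 | 0.65 × 25/24 = 0.677 | 19% | 26% |
| 28 | 0.6 | 0.80 × 25/24 = 0.833 | 30% | 35% |
| 28 | 0.8 | 0.90 × 25/24 = 0.938 | 52% | 55% |
| 28 | 0.9 | 0.95 × 25/24 = 0.990 | 81% | 82% |
| 40 | 0.6 | 0.80 × 37/36 = 0.822 | 41% | 48% |
| 40 | 0.8 | 0.90 × 37/36 = 0.925 | 68% | 72% |
| 20 | 0.9 | 0.95 × 17/16 = 1.009 | 66% | 65% |

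The gain is about a third of the variance at low r, small at high r, and slightly negative in the last row. The arm main effect is a poor test throughout: at N=28 and r=0.6–0.8 its power for the same effect is 10–11%.

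**2. Chance baseline imbalance.** If the arms differ by D at baseline and there is no effect, the expected difference in post scores is rD. The difference in change is then rD − D = −(1−r)D. The standard error of D is √(4/N), which is 0.378 at N=28 and 0.316 at N=40. Take an imbalance of 1.5 standard errors. A baseline t-test gives p of about 0.14–0.15, and this size or larger arises in about 13% of trials per outcome.

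- N=28: D = 0.567 SD, and the shift at r=0.6–0.8 is 0.567 × (0.4 to 0.2) = 0.23 to 0.11 SD.
- N=40: D = 0.474 SD, and the shift is 0.474 × (0.4 to 0.2) = 0.19 to 0.09 SD.

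The adjusted contrast is shifted by about 0. Averaged over all randomisations, both tests hold 5%.

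**3. What the time term would show.** Suppose there is no tDCS effect and both arms change by the same amount s. The time test has non-centrality s√N/√[2(1−r)] on N−2 degrees of freedom. With s = 0.3 SD and r=0.6–0.8, it is significant in 40–68% of trials at N=28 and 54–83% at N=40. Arm-by-time stays at 5%.

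**The case against.** **Arm-by-time is plainly intended and is valid.** The trial is described as randomised and sham-controlled, the text speaks of changes, and arm is crossed with time. This is the natural reading, and the test holds its 5% level. A reader might infer that the planned analysis is an invalid test of tDCS; it is not. The case for baseline adjustment rests on precision and on protection against chance imbalance.

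**The gain depends on unknown inputs.** This stands. It would be wrong to say without conditions that the data are used inefficiently, given the rows at r=0.9.

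**Reading the time term as efficacy is only a possibility.** This also stands. A reader might infer from the CAMS-R sentence that pre-post change was taken as proof of an MBSR effect. The documents do not say so, and the sentence can be read as describing a measure of uptake. Still, the CAMS-R is one of the eight dependent variables and no term is named, so the ambiguity is real.

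**Regression to the mean.** Because PROMIS depression and anxiety scores determine entry, a reader might infer that any fall in them is largely an artefact of selection. The documents do not support this. They place the self-report baseline assessments after eligibility was met, and with a fresh score and independent error the artefact is about zero. It would matter if the entry score was reused as 'pre', or if errors were correlated between the two occasions. The documents settle neither, and arm-by-time is unaffected at about 5%.

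**A post hoc model should not displace the planned test.** This is right. The data had been analysed when the document was written, across eight outcomes with no multiplicity correction. The adjusted model belongs beside the planned test, labelled as added.

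**Conclusion.** The point holds in a limited form. Only the between-arm contrast is controlled, and the plan does not name the RM-ANOVA term that estimates it. Arm-by-time is a sound choice but ignores baseline. Under the assumed values it carries a shift of roughly 0.1–0.2 SD after an unremarkable baseline imbalance. At N=28, adjustment would reduce its variance by about 32% at r=0.3, 6–17% at r=0.6–0.8 and 1% at r=0.9; there is no gain at N=20 and r=0.9. The time term cannot be attributed to MBSR or to the combination, whatever its p-value.

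All of these sizes depend on the assumed N and r and on equal variances. That only tDCS is randomised, that no efficacy term is named and that no baseline covariate is used come directly from the text. This is an improvement worth considering: efficacy is preliminary here and the primary aim is untouched.

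**What to change.** For each of the eight outcomes:

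1. Name arm-by-time as the planned test of tDCS and keep it as such.
2. Add a model of the post score on arm, that outcome's baseline value and site (because randomisation was blocked within site). Report the arm difference with a 95% CI, labelled as added after the planned analysis.
3. Report pre-post changes, including the CAMS-R, as estimates with 95% CIs. State that they are uncontrolled and cannot be attributed to MBSR or to MBSR plus tDCS.

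For PROMIS depression and anxiety, also state whether 'pre' is the entry score or the assessment made after eligibility.

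The cost is eight extra models on data already collected, one or two degrees of freedom in each (baseline slope and site), and some reporting text. The added models must carry a post hoc label, and the sponsor gives up attributing pre-post change to the programme.
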